7.4.4 Deaths

Deaths that occur during the protocol-specified AE reporting period that are attributed by the investigator solely to progression of disease will be recorded on the "Trial Discontinuation" eCRF and should not be reported as a SAE. All other on- trial deaths, regardless of attribution, will be recorded on an SAE Report and expeditiously reported to the Sponsor.

When recording a serious adverse event with an outcome of death, the event or condition that caused or contributed to the fatal outcome should be recorded as the single medical concept on the SAE report and Adverse Event page of the eCRF. If the cause of death is unknown and cannot be ascertained at the time of reporting, record "Death NOS" on the CRF Adverse Event page.

7.4.5 Hospitalization, Prolonged Hospitalization, or Surgery

Any AE that results in hospitalization of >24 hours or prolonged hospitalization should be documented and reported as an SAE unless specifically instructed otherwise in this protocol. There are some hospitalization scenarios that do not require reporting as an SAE when there is no occurrence of an AE. (See section 7.3)

7.4.6 Pre-existing Medical Conditions

A pre-existing medical condition is one that is present at the start of the trial. Such conditions should be recorded on the General Medical History eCRF. A pre-existing medical condition should be recorded as an AE or SAE only if the frequency, severity, or character of the condition worsens during the trial. When recording such events on an SAE Report Form and/or AE eCRF, it is important to convey the concept that the pre-existing condition has changed by including applicable description.

7.4.7 Pregnancy, Abortion, Birth Defects/Congenital Anomalies

Pregnancy, abortion, birth defects, and congenital anomalies are events of special interest. Please refer to pregnancy Section 7.5.1 for specific instructions.

7.4.8 New Cancers

The development of a new primary cancer should be regarded as an AE and will generally meet at least one of the serious criteria. New primary cancers are those that are not the primary reason for the administration of the study treatment and have developed after the inclusion of the patient into the study. They do not include new lesions of the original cancer. Symptoms of metastasis or the new lesions itself should not be reported as an AE/SAE, as they are considered to be disease progression.

7.4.9 Lack of Efficacy

When there is deterioration in the condition for which the study treatment is being used, there may be uncertainty as to whether this is lack of efficacy or an AE. In such cases, unless the sponsor or reporting physician considers the study treatment contributed to the deterioration of the condition, the deterioration should be considered lack of efficacy and not an AE.

7.5 Protocol-Defined Events of Special Interest

The following are events of special interest, and will need to be reported expeditiously.

7.5.1 Pregnancy, Abortion, Birth defects/Congenital anomalies

Female patients who are not of child-bearing potential (see Appendix B) and female patients of child-bearing potential who have a negative pregnancy test within 72 hours prior to C1D1 are eligible for the study. Female patients of child-bearing potential (see Appendix B), and all male partners must consent to use a medically acceptable method of contraception throughout the study period and for 4 weeks after the last dose of Tenalisib. An approved barrier method of contraception must be discussed with the investigator and documented in source note.

During the course of the trial, all female patients of childbearing potential and pregnant partner of male subjects must contact the treating investigator immediately if they suspect that they may be pregnant (a missed or late menstrual period should be reported to the treating investigator).

If an investigator suspects that a patient may be pregnant prior to administration of trial drug(s), the trial drug(s) must be withheld until the result of the pregnancy test is confirmed. If a pregnancy is confirmed, the patient must not receive any trial drug(s), and must be discontinued from the trial. The outcome of the pregnancy will be monitored as outlined in Appendix B.

If an investigator suspects that a patient may be pregnant after the patient has been receiving trial drug(s), the trial drug(s) must immediately be withheld until the result of the pregnancy test is confirmed. If a pregnancy is confirmed, the trial drug(s) must be immediately and permanently stopped, the patient must be discontinued from the trial, and the investigator must notify the Medical Monitor and Sponsor Representative as soon as possible. If a patient becomes pregnant while enrolled in the trial, a Pregnancy Form should be completed and faxed to the Sponsor. The outcome of the pregnancy will be monitored as outlined in Appendix B.

Congenital anomalies/birth defects always meet SAE criteria, and should therefore be expeditiously reported as an SAE, using the previously described process for SAE reporting. A Pregnancy Form should also have been previously completed, and will need to be updated to reflect the outcome of the pregnancy.

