4 SELECTION AND WITHDRAWAL OF SUBJECTS

4.1 Inclusion Criteria

1. Age ≥ 18 years on the day of signing informed consent.
2. Pathologically confirmed T-cell lymphoma at the enrolling institution*.
3. Disease status as defined as relapsed after or refractory to at least one systemic therapy.

4. The patients should have received NOT more than three prior systemic combination chemotherapies.
5. Must have ECOG performance status ≤ 2 .
6. PTCL patients must have measurable disease as defined at least one bi-dimensional measurable lesion with minimum measurement of > 1.5 cm in the longest diameter.
7. Life expectancy of at least 3 months.
8. Toxicities related to prior therapy must have returned to **Grade 1 or less**, except for alopecia.
9. Adequate bone marrow, liver and renal function in line with below mentioned laboratory requirements. Hemoglobin and platelet requirements should not be met by use of recent transfusion or growth factor support (GCSF or erythropoietin) within 3 weeks prior to treatment initiation.
 - Hemoglobin ≥ 8.0 g/dL
 - Absolute neutrophil count (ANC) $\geq 1,000/\mu\text{L}$
 - Platelet count $\geq 75,000/\mu\text{L}$
 - Total bilirubin ≤ 1.5 times the ULN (or $\leq 3 \times$ ULN, if patient has Gilbert syndrome)
 - AST (SGOT) and ALT (SGPT) $\leq 3 \times$ ULN; ≤ 5 ULN in case of liver involvement
 - Calculated creatinine clearance (CrCl) > 50 ml/min by Cockcroft-Gault formula.
10. Use of an effective means of contraception for women of childbearing potential and men with partners of childbearing potential.
11. Female subject of childbearing potential should have a negative urine or serum pregnancy within 72 hours prior to receiving the first dose of study medication. If the urine test is positive or cannot be confirmed as negative, a serum pregnancy test will be required.
12. Provide written informed consent prior to any study-specific screening procedures.
13. Willingness and capability to comply with the requirements of the study.

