6 TRIAL ASSESSMENT AND PROCEDURE

6.1 Overview

The Schedule of Event (Table 5 and Table 6) summarizes the trial procedures to be performed at each visit and is divided into following.

1. Screening (Day -28 to Day 0)
2. On treatment procedures (C1D1 to C7D28)
3. End of Treatment (C8D1 or within 7 days from the last dose)
4. End of Study (Day +30 from the last dose)

Individual trial procedures are described in detail below. It may be necessary to perform these procedures at unscheduled time points if deemed clinically necessary by the investigator. Multiple procedures may be scheduled at the same time point relative to Tenalisib. Priority should be given to PK collection at the time specified and vital signs should be performed prior to blood collections.

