7.7.2 Dose modifications

The dose modification guidelines are intended to be applied when the investigator determines the events to be related to either one of the investigational product.

- *In case the investigator determines the events to be related to Romidepsin, Tenalisib can be continued depending on toxicity at discretion of investigator.*
- *Similarly, in case the investigator determines the events to be related to Tenalisib, Romidepsin can be continued depending on toxicity at discretion of investigator.*
- *In case the event is possibly related to Romidepsin as well as Tenalisib, the most conservative approach of dose modification should be used.*

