Appendix B: Contraceptive Guidelines and Pregnancy

Women Not of Childbearing Potential are defined as Follows
Women are considered post-menopausal and not of child bearing potential if they have had 12 months of natural (spontaneous) amenorrhea with an appropriate clinical profile (e.g. age appropriate, history of vasomotor symptoms) or six months of spontaneous amenorrhea with serum FSH levels > 40 mIU/mL] or have had surgical bilateral oophorectomy (with or without hysterectomy) at least six weeks ago. In the case of oophorectomy alone, only when the reproductive status of the woman has been confirmed by follow up hormone level assessment is she considered not of child bearing potential.
Contraceptive Guidelines for Women of Child-Bearing Potential
Women of child-bearing potential, defined as all women physiologically capable of becoming pregnant, must use highly effective contraception during the study and for 5 T1/2 (48 hrs) plus an additional 4 weeks after stopping treatment . The highly effective contraception is defined as either:

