
 1. True abstinence: When this is in line with the preferred and usual lifestyle of the subject. Periodic abstinence (e.g., calendar, ovulation, symptothermal, post-ovulation methods) and withdrawal are not acceptable methods of contraception. 2. Sterilization: have had surgical bilateral oophorectomy (with or without hysterectomy) or tubal ligation at least six weeks ago. In case of oophorectomy alone, only when the reproductive status of the woman has been confirmed by follow up hormone level assessment. 3. Male partner sterilization (with the appropriate post-vasectomy documentation of the absence of sperm in the ejaculate). For female subjects on the study, the vasectomised male partner should be the sole partner for that patient. 4. Use of a combination of any two of the following (a+b): 
 a. Placement of an intrauterine device (IUD) or intrauterine system (IUS). b. Barrier methods of contraception: Condom or Occlusive cap (diaphragm or cervical/vault caps) with spermicidal foam/gel/film/cream/vaginal suppository. 
The following are unacceptable forms of contraception for women of childbearing potential:
 
 • Oral contraception, injected or implanted hormonal methods are not allowed as Tenalisib may potentially decrease the effectiveness of hormonal contraceptives. • IUD progesterone T • Female condom • Natural family planning (rhythm method) or breastfeeding • Fertility awareness • Withdrawal • Cervical shield 
Women of child-bearing potential must have a negative serum or urine pregnancy test ≤ 72 hours prior to initiating treatment.

Fertile Males
Fertile males, defined as all males physiologically capable of conceiving offspring must use condom during treatment, plus additional 12 weeks after stopping treatment and should not father a child in this period.
Pregnancies

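### Section 7.5.1 and Appendix B of the Protocol set different post-treatment contraception periods, counted from different starting points, and nothing says which governs

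*Protocol*

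**What the plan says.** Three places in the Protocol deal with contraception.

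- Inclusion criterion 10 (Section 4.1) asks for "Use of an effective means of contraception for women of childbearing potential and men with partners of childbearing potential". It gives no duration.
- Section 7.5.1 names female patients of child-bearing potential "and all male partners must consent to use a medically acceptable method of contraception", to be used "throughout the study period and for 4 weeks after the last dose of Tenalisib". It points to Appendix B for the definition of child-bearing potential and for following a pregnancy to its outcome, but not for how long contraception lasts.
- Appendix B requires women of child-bearing potential to use highly effective contraception during the study and "for 5 T1/2 (48 hrs) plus an additional 4 weeks after stopping treatment". For men it says "Fertile males, defined as all males physiologically capable of conceiving offspring must use condom during treatment", then "plus additional 12 weeks after stopping treatment".

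Section 7.7.2 adds that, when an event is judged related to Tenalisib, "Romidepsin can be continued depending on toxicity at discretion of investigator". The two drugs can therefore stop at different times.

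**The concern.** The trial gives two drugs, yet 7.5.1 counts its post-treatment period from one of them, while Appendix B counts from the end of treatment. The lengths differ as well, and no sentence ranks one text above the other. A site that works from the safety section and a site that works from the appendix could give different instructions to patients in the same position.

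The group covered is also unclear. Section 7.5.1 speaks of male partners and Appendix B of fertile males. A reader cannot be sure whether a male patient falls under the first rule, the second, or both. This is an instruction meant to protect a fetus, so a site should not have to choose between two versions.

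**Working it through.** No sample size, power or error rate is involved. The check sets the passages side by side and converts each period to days.

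| | Section 7.5.1 | Appendix B |
|---|---|---|
| Women | study period, and 4 × 7 = 28 days | 48 h + 4 weeks = 2 + 28 = 30 days |
| Men | 28 days if male patients are covered; otherwise none stated for them | 12 × 7 = 84 days |
| Counted from | last dose of Tenalisib | stopping treatment (no drug named) |

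**Tenalisib's last dose is also the end of treatment.** This is the case for a patient who completes the planned course. Seven 28-day cycles end on Day 7 × 28 = 196, and the last Romidepsin infusion (Cycle 7 Day 15) falls on Day 6 × 28 + 15 = 183.

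- Women: 30 − 28 = 2 days.
- Men, if male patients are covered by 7.5.1: 84 − 28 = 56 days.

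**Effect of the study period.** Section 7.5.1 does not define it. The schedules of events (Tables 5 and 6) put C8D1 at Day 197 and End of Study at Day 227, and 227 − 197 = 30. Section 6.1 places End of Study 30 days after the last dose. If the study period runs to that visit, 7.5.1 already covers 30 days. The women's difference is then 30 − 30 = 0, and the men's is 84 − 30 = 54 days, again only if male patients are covered.

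**Tenalisib stops first and Romidepsin continues to Day 183.** Take Appendix B's end of treatment as the last dose of either drug, which is an assumption because it names none. Suppose Tenalisib stops so early that its 4 weeks are over before Day 183. Then only the study-period clause of 7.5.1 still applies.

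- Study period ends at C8D1: 197 − 183 = 14 days after the last Romidepsin dose, against 30 (women) or 84 (men) in Appendix B.
- Study period ends 30 days after the last dose: 30 days, against the same 30 or 84.

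This case is foreseeable. Table 8 requires permanent discontinuation of Tenalisib for some hepatic events. Section 1.1.2 reports 12 treatment-related Grade 3 or higher AST/ALT elevations in a study of 58 treated patients, although it does not say how many led to stopping.

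**The case against.** **The conflict for men may not exist.** In its sentence, the phrase on male partners most naturally means partners of female patients. The next paragraph of 7.5.1 uses a different term for men in the trial. Appendix B's rule for fertile males runs during and after treatment, which suits male patients. On that reading the two rules cover different people, and male patients have a single stated period, in the appendix. This largely stands, so the 56 days is conditional. It does not remove the ambiguity. Section 7.5.1 also deals with pregnant partners of male subjects, and Appendix B defines fertile males without limiting them to patients.

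**A patient on Romidepsin is still in the study.** A reader might infer a long unprotected interval. For example, if Tenalisib stops on Day 30 (an illustrative day), its 4 weeks end on Day 30 + 28 = 58, which is 183 − 58 = 125 days before the last Romidepsin dose. The documents do not support that inference. The two clauses of 7.5.1 are cumulative, so contraception is still required while the patient remains on study treatment. Only the time after the last Romidepsin dose is in question.

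**Section 7.5.1 is not shown to be too short.** A reader might conclude that its period is inadequate or that it counts from the wrong drug. Nothing in the Protocol establishes which period or starting point is correct; the texts only differ. Consent pages are not in the copy reviewed, so what patients are told is unknown.

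**Appendix B is the dedicated guideline.** When treatment ends with Tenalisib, following it also satisfies the 4-week clause. That is a sensible default, but no text makes it the governing rule.

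**Conclusion.** The two texts disagree on duration and starting point, and the Protocol does not say which governs. The size depends on the reading:

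- **Women:** 2 days when Tenalisib's last dose ends treatment, and none if the study period runs to End of Study. If Tenalisib stops well before Romidepsin and the study period ends at C8D1, 7.5.1 gives 14 days after a Day 183 infusion, against 30 in Appendix B.
- **Men:** 56 days (54 if the study period runs to End of Study), but only if 7.5.1 is read to include male patients. Otherwise 7.5.1 is silent on them and Appendix B alone applies.

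This is a minor point, but more than clerical, because it is a safety instruction in a two-drug trial where one drug may outlast the other. It changes no endpoint, estimate or sample size.

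**What to change.** Reconcile Section 7.5.1, Appendix B and inclusion criterion 10 so that each group (female patients, male patients, and male partners of female patients if they are meant separately) has one stated duration and one stated starting point. The starting point should be explicit about the case where one study drug continues after the other stops. State whether the 7.5.1 sentence covers male patients, and either define the study period there or remove the term. The simplest drafting is to state the rule once and refer to it elsewhere. The sponsor sets the durations and the starting point; none is proposed here.

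The cost is amendment wording, plus a check that the consent form agrees. No data collection or analysis changes.

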7.5.2 Overdose

An overdose is defined as accidental or intentional administration of any dose of product that is considered both excessive and medically important. For purposes of this trial, an overdose will be defined as any dose exceeding the proposed dose of Tenalisib (e.g. > 400 mg in first cohort) and/or prescribed dose for Romidepsin.

Symptomatic and non-symptomatic overdose must be reported in the CRF. Any accidental or intentional overdose with the trial treatment that is symptomatic, even if not fulfilling a seriousness criterion, is to be reported to the Sponsor immediately as an AE. All symptomatic overdose, fulfilling a seriousness criterion, is to be reported as an SAE as per the SAE reporting procedure. For patients who experience overdose, treatment should consist of supportive therapy. A decision to interrupt treatment or dose reduction to be taken depending on the symptoms.

7.6 Dose-Limiting Toxicity

All toxicities should be considered to be related to either Tenalisib/ Romidepsin combination or to either Tenalisib or Romidepsin individually unless there is a clear alternative explanation. Toxicity will be considered dose-limiting if it occurs during the first cycle (28 days) treatment and is considered related to the combination. Toxicity will be assessed utilizing the National Cancer Institute Common Terminology Criteria for Adverse Events (NCI CTCAE) v5.0. **Dose-limiting toxicities are defined as the following:**

7.6.1 Hematological DLTs

- Grade 4 neutropenia that does not resolve to \leq Grade 3 within 14 days with supportive treatment (e.g. growth factors) **OR** Grade ≥ 3 Febrile neutropenia (ANC $<1000/\mu\text{L}$ with fever $>38.5^\circ\text{C}$ [101°F] that does not resolve to \leq Grade 2 within 14 days with supportive treatment.

- Grade 4 thrombocytopenia that does not resolve to \leq Grade 3 within 14 days with supportive treatment **OR** Grade ≥ 3 thrombocytopenia associated with Grade >2 bleeding that does not resolve to \leq Grade 2 within 14 days with supportive treatment.

7.6.2 Non-Hematological DLTs

- Grade ≥ 3 non-hematologic toxicity that could not be controlled or prevented by supportive care including corticosteroids **with exception of:**
 - Grade ≥ 3 ALT/AST elevation that resolves to \leq Grade 2 within 14 days;
 - Grade ≥ 3 diarrhea that improves \leq Grade 2 within 48 hours **or** Grade ≥ 3 diarrhea in patients who have not received optimal treatment with anti-diarrhoeal drugs.
 - Grade ≥ 3 vomiting in patients who have not received the highest therapeutic dose of antiemetics (e.g. steroids, 5HT3 antagonists, prochlorperazine, lorazepam)
 - Single episode of Grade ≥ 3 infusion reaction.
 - Grade 3 nausea, Grade 3 asthenia or Grade 2 alopecia.
- Treatment delay of ≥ 14 days due to unresolved toxicity.

Adverse events meeting the above definitions but unrelated to study drug will not be considered DLTs. In some instances (e.g. in case of pre-existent Grade 2 toxicity), an event may fall within the protocol definition of a DLT but will not be considered a DLT (i.e., not clinically meaningful/significant or relevant to the combination). In such cases, the SRC will thoroughly review the event, supporting data, and the reasons for not considering the event a DLT will be clearly documented with supporting rationale. Conversely, other events which do not meet the definition of a DLT but are concerning to the SRC may be considered as DLTs.

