7.6.3 Determination of Dose-limiting toxicity

The patient population used for determination of MTD will consist of patients who have met the minimum safety evaluation requirements of the study, and/or who have experienced a DLT. The data of at least 3 patients will be required for DLT assessment.

- DLT assessment period will be 28-days (inclusive) (will begin on C1D1 and end on C2D1), unless extended by the medical monitor.
- Patients must have been treated with at least 2 doses of Romidepsin and minimum 14 days with Tenalisib in the first cycle to be considered eligible for safety assessment unless identified to have a DLT.
- *Patients experiencing DLT after initiating combination will be considered evaluable regardless of the number of doses received (Please note Romidepsin alone will be administered on Day 1, therefore patient will not be considered for MTD assessment if patient develops DLT on these days).*

If a patient withdraws from the study during Cycle 1 due to any reason other than DLT (e.g. disease progression or consent withdrawal) and does not meet the minimum requirements for inclusion in the MTD-determining population described above will be replaced.

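### Two DLT exceptions have no upper grade, so a Cycle 1 liver or diarrhea event that permanently ends Tenalisib may go uncounted in the escalation rule

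*Protocol*

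**What the plan says.** Protocol 7.6.2 defines a non-hematological DLT as a Grade 3 or higher toxicity "that could not be controlled or prevented by supportive care including corticosteroids", and then lists exceptions. Two of them matter here.

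- Liver: Grade 3 or higher "ALT/AST elevation that resolves to" Grade 2 or less within 14 days.
- Diarrhea: Grade 3 or higher that improves to Grade 2 or less within 48 hours, or Grade 3 or higher "diarrhea in patients who have not received optimal treatment with anti-diarrhoeal drugs".

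Neither has an upper grade. Another item in the same list names exact grades: "Grade 3 nausea, Grade 3 asthenia or Grade 2 alopecia". A separate criterion makes a treatment delay of at least 14 "days due to unresolved toxicity" a DLT. The section closes by saying that "other events which do not meet the definition of a DLT but are concerning to the SRC may be considered as DLTs".

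Protocol 7.6.3 sets evaluability. A patient needs at least two Romidepsin doses and a "minimum 14 days with Tenalisib in the first cycle to be considered eligible for safety assessment unless identified to have a DLT".

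Table 8 (Protocol 7.7.2.1) requires permanent discontinuation of Tenalisib for ALT/AST above 20 x ULN and for life-threatening diarrhea.

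Protocol 3.2.1.1 ties escalation to DLTs as Section 7.6 defines them. The SAP tabulates DLTs (10.6.2) and repeats the evaluability rule (5.1), but it has no DLT definition of its own and adds no cap.

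**The concern.** The DLT count is the only formal input to the 3+3 decision. An event severe enough that the protocol bars the patient from any further Tenalisib is strong evidence about the tolerability of that dose level, yet the written definition can leave it out. Whether it counts then depends on an SRC decision that the protocol allows but does not require.

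The liver exception matters more. AST/ALT elevation is the most frequent treatment-related Grade 3 or higher event listed for Tenalisib in study RP6530-1401 (Protocol 1.1.2), so the open-ended exemption covers the drug's main known toxicity. The top cohort also deserves care. Under 3.2.1.1, 800 mg BID with 14 mg/m² is taken as optimal if no DLT is seen there, and the 24-patient expansion follows at the chosen dose.

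**Working it through.** The protocol states no figure to reproduce, so the check mainly sets the rules side by side. The arithmetic only illustrates the consequence.

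**1. Exemption against stopping rule**

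| Related Cycle 1 event | DLT under 7.6.2? | Table 8 action |
|---|---|---|
| ALT/AST >20 x ULN, falls to Grade 2 or less within 14 days | Exempt | Permanent Tenalisib stop |
| Life-threatening diarrhea, Grade 2 or less within 48 hours | Exempt | Permanent Tenalisib stop |
| Life-threatening diarrhea, not optimally treated | Exempt | Permanent Tenalisib stop |

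Table 8 grades diarrhea in words rather than numbers. The comparison does not depend on the mapping, because an exception for Grade 3 or higher covers every greater severity.

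**2. The opening condition is a second cause.** A Grade 4 ALT/AST rise brought down with corticosteroids may fall outside the definition before any exception is reached. A cap alone would not close the gap.

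**3. Evaluability.** In Cycle 1 of dose escalation Tenalisib starts on Day 3 (Protocol 5.1), so the 14th dosing day is 3 + 14 − 1 = Day 16. A patient with an exempt event who stops before completing Day 16 may not be MTD-evaluable. One who stops later, with two Romidepsin doses given, counts as DLT-free. The replacement sentence in 7.6.3 covers patients who withdraw from the study. It does not clearly cover one who stops Tenalisib and stays on Romidepsin, which 7.7.2 permits.

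**4. Effect on a single cohort.** One uncounted event turns 1/3 into 0/3 (escalate without adding three patients) or 2/6 into 1/6 (escalate instead of declaring the MTD exceeded).

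**5. Prior liver signal.** The listed related Grade 3 or higher events in RP6530-1401 sum to 12 + 4 + 2 + 7 × 1 = 25. AST/ALT elevation is 12/25 = 48% of them, or 12/58 = 20.7% of patients (exact 95% CI 11.2% to 33.4%) if n counts patients. This covers all doses and any cycle. Grade 4 share, timing and recovery are not given.

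**6. Illustration only; all rates are assumed.** Let p be the counted DLT rate. The 3+3 escalation probability is E(p) = (1−p)³ + 3p(1−p)⁵. At p = 0.20, E = 0.512 + 0.197 = 0.709. Let exempt events occur in a further proportion q of patients, distinct from those with counted DLTs, and let the SRC never use its discretion.

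| q | As written, exempt patients evaluable: E(0.20) | As written, exempt patients replaced: E(0.20/(1−q)) | Events counted: E(0.20+q) | Gap, points |
|---|---|---|---|---|
| 1% | 70.9% | 70.4% (p = 0.2020) | 68.7% | 1.7–2.2 |
| 2% | 70.9% | 70.0% (p = 0.2041) | 66.5% | 3.5–4.4 |
| 5% | 70.9% | 68.6% (p = 0.2105) | 60.0% | 8.6–10.9 |

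The two as-written columns bracket the evaluability question; full replacement is an assumption, for the reason in step 3. Counting the event does not by itself stop escalation. After 1/3, the chance that the next three patients are clear is (1−p)³ = 0.493, 0.475 or 0.422 at p = 0.21, 0.22 or 0.25.

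**The case against.** **The SRC is the safeguard.** It reviews safety before each escalation (Protocol 3.6.1) and may count any event that concerns it. The error needs an SRC that sees a Tenalisib-ending Cycle 1 event and lets it pass. This stands as a strong mitigation and is why the average effect is probably modest. It does not define the rule, though. Removing a DLT from the count needs a documented rationale; leaving an exempt event uncounted needs none.

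**The delay criterion may catch it.** It requires a delay of at least 14 days caused by toxicity that has not resolved. The events at issue can have resolved, and the text does not say whether a permanent stop is a delay.

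**The symbol may be loose notation.** Table 8 labels the band from above 5 to 20 x ULN as Grade ≥ 3, so 7.6.2 might mean Grade 3 only. But Table 8 prints the range beside each label. Section 7.6.2 prints none, and its own opening condition uses the same symbol in the ordinary open-ended sense.

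**The two sections serve different purposes.** A reader might infer that 7.6.2 and Table 8 contradict each other. They do not. One governs cohort escalation, the other individual dosing, and both can be followed at once; 7.7 even lets a patient resume Tenalisib after a DLT. What remains is a difference in thresholds that lets a drug-ending event go uncounted.

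**All four open-ended exceptions might seem to share the problem.** The vomiting exception, for patients "vomiting in patients who have not received the highest therapeutic dose of antiemetics", and the single infusion reaction also lack an upper grade. Table 8 sets no specific permanent stop for either: vomiting falls under the general hold-and-reduce row at first occurrence, and infusion reactions have no row. Deaths attributed to study drug are handled in 3.6.2. None of these belongs to the defect.

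**Conclusion.** The point holds for two events: related Cycle 1 ALT/AST above 20 x ULN that recovers to Grade 2 or less within 14 days, and life-threatening diarrhea that improves within 48 hours or was not optimally treated. Both the missing upper grade and the supportive-care condition contribute. The consequence can change the decision for a single cohort, while the average effect is unknown.

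A reader might take the 1.7 to 10.9 point gaps as estimates of bias. They are not. They rest on an assumed 20% counted rate, assumed exempt rates of 1% to 5% and an SRC that never intervenes, so for those rates they are upper bounds. The RP6530-1401 summary cannot supply better inputs: it lists no AST/ALT event among the related SAEs and no diarrhea among the related Grade 3 or higher events, although a Grade 4 laboratory value need not be an SAE.

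Nor does the primary AE endpoint suffer, since these events are still reported as AEs. The issue is confined to the DLT count, the MTD-evaluable set and the escalation decision built on them. It should be fixed because the correction is small and bears on patient safety.

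**What to change.** Amend Protocol 7.6.2 in two places.

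1. Cap the ALT/AST and diarrhea exceptions at Grade 3.
2. Add a sentence: a related Cycle 1 ALT/AST elevation above 20 x ULN, or related Cycle 1 life-threatening diarrhea, arising after the combination starts and for which Table 8 mandates permanent Tenalisib discontinuation, is a DLT regardless of the supportive-care condition and makes the patient evaluable under 7.6.3.

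Put a matching line in 7.6.3. Keep the SRC's documented power to declassify an event and the rule excluding events on Romidepsin alone. The added sentence should name these two events. A general clause covering every mandated discontinuation would also reach recurrence-based hematologic stops and Romidepsin stops, which are outside this point. Capping vomiting and infusion reactions at Grade 3 is an optional consistency edit.

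No new data or visits are needed. The downside is that a few events now exempt would count, so a cohort may expand or stop slightly more often.
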